2. SUMMARY OF CHANGES

Not applicable.

4. SYNOPSIS

Name of Sponsor/Company: Endo Pharmaceuticals Inc.	
Name of Investigational Product: EN3835	
Name of Active Ingredient: Collagenase clostridium histolyticum	
Title of Study: A Phase 2 Open-label Study of EN3835 in the Treatment of Edematous Fibrosclerotic Panniculopathy	
Lead Principal Investigator: TBD	
Study Period: Estimated date first subject enrolled: Nov-2017 Estimated date last subject completed: Jul-2018	Phase of Development: 2
Objectives: Primary Objective: 
 To assess the safety of EN3835 in the treatment of edematous fibrosclerotic panniculopathy (EFP), commonly known as cellulite, in adult women Secondary Objective: 
 To assess effectiveness of EN3835 in the treatment of EFP 	
Study Design: This study is a Phase 2, open-label study of safety and effectiveness of EN3835 in the treatment of EFP in adult women. Subjects will be screened for study eligibility within 14 days prior to enrolling in this study. Subjects with at least 2 bilateral treatment areas (bilateral buttocks or bilateral posterolateral thighs) (also referred to as a region) (eg, their left and right buttocks or left and right posterolateral thighs) with mild, moderate or severe levels of cellulite as assessed by the Investigator using the Clinician Reported Photonumeric Cellulite Severity Scale (CR-PCSS) and a Hexsel Cellulite Severity Scale no greater than 13 will be eligible. If both their left and right buttocks AND left and right posterolateral thighs are eligible, one pair will be randomly selected as the assigned treatment areas. Subjects will receive an open-label treatment course which consists of up to 3 treatment visits (ie, Day1, Day 22, and Day 43). Each treatment visit will consist of 12 injections (0.3 mL per injection of EN3835 0.07 mg/injection) in each of the treatment areas of the region for a total volume of 7.2 mL (1.68 mg). Selection of dimples to be treated in the assigned treatment areas will be at the discretion of the Investigator. End-of-study will occur at study Day 180. At each treatment visit, the Investigator will first conduct a live assessment of each treatment area of the assigned region using the CR-PCSS. The Investigator will then select and mark the dimples to be treated within each treatment area. All the assessments must be done before marking the dimples for injection. At Day 180 (End of Study/Early Termination), The Investigator will conduct live assessments of each of the treatment area using the CR-PCSS. The subject will complete the Subject Satisfaction with Cellulite Treatment assessment. In a photographic sub-study at two sites, subjects will return to the site to have their treated areas photographed at 1, 3, 6, and 13 days after each treatment visit to assess local site reactions post-injection.	
Number of Subjects (planned): Up to 150	
Study Center(s): Approximately 10 sites in United States	

Name of Sponsor/Company: Endo Pharmaceuticals Inc.
Name of Investigational Product: EN3835
Name of Active Ingredient: Collagenase clostridium histolyticum

Diagnosis and Inclusion/Exclusion Criteria:
 
Inclusion Criteria:
 
 1. Voluntarily sign and date an informed consent agreement 2. Be a female ≥ 18 years of age 3. At Screening visit, have at least one treatment region (bilateral buttocks or bilateral posterolateral thighs), with each region treatment area having: 
 a. a score of 2 (mild) or greater as reported by the Investigator (CR-PCSS), and b. a Hexsel CSS score no greater than 13 4. Be willing to apply sunscreen to the assigned treatment areas before each exposure to the sun while participating in the study (ie, Screening through end of study) 5. Be judged to be in good health, based upon the results of a medical history, physical examination, and laboratory profile at Screening 6. Have a negative serum pregnancy test at Screening and a negative urine pregnancy test before injection of study drug and be using a stable and effective contraception method (eg, abstinence, intrauterine device [IUD], hormonal [estrogen/progestin] contraceptives, or double barrier method) for at least 1 menstrual cycle prior to study enrollment and for the duration of the study; or be menopausal defined as 12 months of amenorrhea in the absence of other biological or physiological causes, as determined by the Investigator; or post-menopausal for at least 1 year; or be surgically sterile 7. Be willing and able to cooperate with the requirements of the study 8. Be able to read, complete and understand the patient-reported outcomes rating instruments in English 
Exclusion Criteria:
 
A subject will be excluded from study participation if she:
 
 1. Has any of the following systemic conditions: 
 a. Coagulation disorder b. Evidence or history of malignancy (other than excised basal-cell carcinoma) unless there has been no recurrence in at least 5 years c. History of keloidal scarring or abnormal wound healing d. Concurrent diseases or conditions that might interfere with the conduct of the study, confound the interpretation of the study results, or endanger the subject's well-being. Any questions about concurrent diseases should be discussed with the Medical Monitor. e. Evidence of clinically significant abnormalities on physical examination, vital signs, electrocardiogram (ECG), or clinical laboratory values 2. Has any of the following local conditions in the area to be treated: 
 a. History of lower extremity thrombosis or post-thrombosis syndrome b. Vascular disorder (eg, varicose veins, telangiectasia) in area to be treated c. Inflammation or active infection d. Active cutaneous alteration including rash, eczema, psoriasis, or skin cancer e. Has a tattoo and/or a mole located within 2 cm of the site of injection 3. Requires the following concomitant medications before or during participation in the trial: 
 a. Anticoagulant or antiplatelet medication or has received anticoagulant or antiplatelet medication (except for ≤ 150 mg aspirin daily) within 7 days before injection of study drug

Name of Sponsor/Company: Endo Pharmaceuticals Inc.
Name of Investigational Product: EN3835
Name of Active Ingredient: Collagenase clostridium histolyticum

4. Has used any of the following for the treatment of EFP on the legs or buttocks within the timelines identified below or intends to use any of the following at any time during the course of the study:
 
 Liposuction in the areas of the body selected for treatment during the 12-month period before injection of study drug Injections (eg, mesotherapy); radiofrequency device treatments; laser treatment; buttock and/or thigh implant treatment, cryolipolysis, or surgery (including subcision and/or powered subcision) within the assigned treatment areas during the 12-month period before injection of study drug Endermologie or similar treatments within the assigned treatment areas during the 6-month period before injection of study drug Massage therapy within the assigned treatment areas during the 3-month period before injection of study drug Creams (eg, Celluverta™, TriLastin®) to prevent or mitigate EFP within the assigned treatment areas during the 2-week period before injection of study drug 
5. Is presently nursing or providing breast milk
 
6. Intends to become pregnant during the study
 
7. Intends to initiate an intensive sport or exercise program during the study
 
8. Intends to initiate a weight reduction program during the study
 
9. Intends to use tanning spray or tanning booths during the study
 
10. Has received an investigational drug or treatment within 30 days before injection of study drug
 
11. Has a known systemic allergy to collagenase or any other excipient of study drug
 
12. Has received any collagenase treatments at any time prior to treatment
 
13. Was a subject in a previous cellulite clinical trial of collagenase clostridium histolyticum (CCH): AUX-CC-830, AUX-CC-831, EN3835-102, EN3835-104, EN3835-201, and/or EN3835-202
 
14. Any other condition(s) that, in the Investigator's opinion, might indicate the subject to be unsuitable for the study


Investigational Product, Dosage and Mode of Administration: EN3835, 1.68 mg, subcutaneous. A dose of 0.84 mg of EN3835 per treatment area will be administered as 12 subcutaneous injections (0.3-mL injection administered as three 0.1-mL aliquots per injection) in each of two treatment areas for a total dose of 1.68 mg and a total volume of 7.2 mL (3.6 mL per treatment area). Total number of injections will be 24 injections per treatment visit into the assigned region (left and right buttocks or left and right posterolateral thighs). There will be 3 treatment visits at 21-day intervals, ie, treatments on Days 1, 22, and 43 will be administered.

Duration of Study: Up to 194 days (includes screening phase)
 
Screening Phase: Up to 14 days

Name of Sponsor/Company: Endo Pharmaceuticals Inc.
Name of Investigational Product: EN3835
Name of Active Ingredient: Collagenase clostridium histolyticum

Criteria for Evaluation:
 
Safety:
 
Safety will be assessed throughout the study through the recording of:
 
 • Adverse events (AEs) (including those of special interest (AESI); which are adverse events such as [REDACTED]) • Vital signs • Clinical laboratory tests • Immunogenicity assessment (ie, assessed through the determination of binding and neutralizing anti-AUX-I and anti-AUX-II antibody levels) 
In addition, injection site reactions/local tolerability in the treated areas (through subject and Investigator reporting) will be assessed.
 
Effectiveness:
 
 • Investigator using the CR-PCSS by live assessment: 5-level scale ranging from 0 (no cellulite) to 4 (severe cellulite) (Day 1 (Baseline) and Days 22, 43, 90, and 180) for each treatment area • Subject satisfaction with cellulite treatment assessment: 5-level scale ranging from 2 (very satisfied) to -2 (very dissatisfied) (Day 180)

Statistical Methods:
 
Sample Size Consideration: To have a sufficient database of subjects establishing safety following exposure to EN3835, up to 150 subjects will be enrolled and monitored for 6 months in accordance with International Conference on Harmonisation (ICH) guidance.
 
Analysis Populations:
 
 • Safety population: The Safety population is defined as all subjects who receive at least 1 injection of EN3835 • Effectiveness population: The effectiveness population is defined as all subjects in safety population with a baseline and 1 post-injection evaluation of the CR-PCSS in at least one treatment area. 
Analyses:
 
Safety Endpoints:
 
The following variables are safety endpoints:
 
 • AEs: Mapped to preferred term using the Medical Dictionary for Regulatory Activities (MedDRA) • Vital signs • Clinical laboratory tests 
AEs will be summarized by proportion of subjects reporting each event. Descriptive statistics will be presented for actual and change from baseline at each visit for vital signs and for each clinical laboratory test parameter.

Name of Sponsor/Company: Endo Pharmaceuticals Inc.
Name of Investigational Product: EN3835
Name of Active Ingredient: Collagenase clostridium histolyticum
Immunogenicity: Anti-AUX-I and anti-AUX-II antibody levels will be summarized using descriptive statistics for the actual value at the visit. Samples from Day 1 and Day 180 will be analyzed for anti-AUX-I and anti-AUX-II and a subset will be analyzed for neutralizing antibodies.
Effectiveness Endpoints: 
• Proportion at each level of improvement in the CR-PCSS of each assigned treatment area (Days 22, 43, 90, and 180):
– Proportion of responders defined as subjects with an improvement in severity from baseline of at least 2 levels of severity in the CR-PCSS– Proportion of responders defined as subjects with an improvement in severity from baseline of at least 1 level of severity in the CR-PCSS• Number of responses at each level of the subject satisfaction with cellulite treatment (Day 180)
All effectiveness endpoints will be summarized as numbers and percentages.

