11.3. Subject Discontinuation Criteria

A premature discontinuation will occur when a subject who signed informed consent ceases participation in the study, regardless of circumstances, prior to the completion of the protocol. Subjects can be prematurely discontinued from the study for one of the following reasons:

- An adverse event
- A protocol violation (reason must be specified, for example: lack of compliance, use of a prohibited concomitant medication, failure to meet inclusion/exclusion criteria after study entry, etc.)
- Withdrawal by subject (reason must be specified)
- The subject was “lost to follow-up”
- Other reasons (reason must be specified, for example: the subject moved, pregnancy, Investigator decision, Sponsor decision to terminate trial, etc.)

If a subject discontinues from the study, all end-of-study procedures should be conducted as detailed in section 5, Schedule of Events. The date a subject discontinues and the reason for discontinuation will be recorded in the source documentation and Electronic Case Report Form (eCRF). If, however, a subject withdraws consent, no end-of-study procedures are required (but are encouraged to reduce missing information) except the collection of adverse event (AE) information. This information should be recorded in the source documentation and the eCRF.

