17.2.2. Effectiveness Population

The effectiveness population is defined as all subjects in Safety Population with a baseline and at least 1 post-injection evaluation of the Investigator CR-PCSS in at least one treatment area. All evaluations of effectiveness will be based on the effectiveness population.

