3.3.1. Safety Population

The safety population is defined as all enrolled subjects who have at least one injection of study medication. All safety parameters will be summarized based on this population.

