3.3.2. Effectiveness Population

The effectiveness population is defined as all subjects in safety population with a baseline and at least 1 post-injection evaluation of the Investigator CR-PCSS in at least one treatment area.

All evaluations of effectiveness will be based on the effectiveness population.

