3.4.6. Effectiveness Evaluation

All analyses for effectiveness evaluation will be conducted in the effectiveness population.

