3.4.6.1.2. Responder Summaries

The investigator CR-PCSS responder classification will be summarized by assigned region (buttock or thigh) and overall (buttock and thigh) at Day 22, Day 43, Day 90, Day 180 (EOS/ET) with counts and percentages for both two-level responders and the one-level responders.

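### The effectiveness population leaves out injected women who are never rated again, and no all-injected summary shows how much the response percentages depend on that

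*Protocol*

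**What the plan says.** Three places define the effectiveness population. The protocol synopsis reads: "The effectiveness population is defined as all subjects in safety population with a baseline and 1 post-injection evaluation of the CR-PCSS". Protocol 17.2.2 has "all subjects in Safety Population with a baseline and at least 1 post-injection evaluation of the Investigator CR-PCSS in at least one treatment area", and SAP 3.3.2 repeats it. The synopsis omits the words 'at least' before the number, but I read all three as one rule.

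SAP 3.4.6 applies it without exception: "All analyses for effectiveness evaluation will be conducted in the effectiveness population". SAP 3.4.6.1.2 asks for responder summaries by region and overall at Days 22, 43, 90 and 180 "with counts and percentages for both two-level responders and the one-level responders". It names no denominator for each visit and no rule for a missing rating. The wider set is already defined in SAP 3.3.1: "The safety population is defined as all enrolled subjects who have at least one injection of study medication". No effectiveness summary uses it.

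On discontinuation, Protocol 11.3 asks that end-of-study procedures be done. Under Protocol 12.7 these include the CR-PCSS and the satisfaction question. The exception is withdrawal of consent, where "no end-of-study procedures are required (but are encouraged to reduce missing information". Protocol 11.3.1 says that discontinued subjects are not replaced.

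**The concern.** Membership depends on something that happens after treatment. A CR-PCSS of 2 or more at Screening is an entry criterion (Protocol 11.1), and SAP 3.2.5.1 takes the baseline from Screening. Every eligible injected woman therefore already has a baseline, and only the lack of a later rating can remove her. The first scheduled post-injection rating is at Day 22.

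Readers will take the responder and satisfaction percentages as describing women who were treated. If those who leave early and unrated did less well than those who stayed, the published percentages flatter the treatment. The study has a single arm (SAP 3.1.3.1), so no control group carries the same selection.

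Such a pattern is plausible. Protocol 8.3 reports injection site bruising in 75.1% and injection site pain in 59.3% of treated women in the Phase 2b study. That study treated one area (Protocol 8.1.3); this one treats two at each visit.

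**Working it through.** **No figure to reproduce.** The plan gives up to 150 subjects (Protocol 17.1, SAP 3.7) with no assumed response rate, dropout rate or precision. The check below is denominator arithmetic.

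**Inputs.**
- N = 150 injected women, the planned maximum.
- k = women with no post-injection rating. The documents give no value, so I assume 3, 8 and 15 (2.0%, 5.3% and 10.0%).
- p = response rate among rated women. The documents give no expected value for this study's CR-PCSS endpoints. I use 50% as a round figure and two Phase 2b results from Protocol 8.1.3 as illustrations: 72.3% (1-level, patient-reported scale) and 10.6% (2-level composite). Neither is this study's endpoint.
- q = response rate among unrated women, which is unknown.

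**Formula.** The reported rate is p. The rate over all injected women is [p(N − k) + qk]/N. The difference is

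bias = (k/N) × (p − q).

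An unrated woman lacks both areas, so the same fraction k/N applies to one side or to both sides pooled.

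**If every unrated woman is a non-responder (q = 0)**, the all-injected rate is p(N − k)/N:

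| Unrated k | p = 10.6% | p = 50% | p = 72.3% |
|---|---|---|---|
| 3 (2.0%) | 10.4% (0.2 points lower) | 49.0% (1.0) | 70.9% (1.4) |
| 8 (5.3%) | 10.0% (0.6) | 47.3% (2.7) | 68.4% (3.9) |
| 15 (10.0%) | 9.5% (1.1) | 45.0% (5.0) | 65.1% (7.2) |

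In counts, for k = 8: 71/142 = 50.0% of rated women, but 71/150 = 47.3% of injected women.

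**If unrated women respond like the rated (q = p)**, the bias is zero for any k.

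**If every unrated woman would have responded (q = 1)**, the sign reverses. At k = 8 the reported rate is too low by (8/150) × (1 − p): 4.8 points at 10.6%, 2.7 at 50% and 1.5 at 72.3%.

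**How many women it takes.** With q = 0, a 2-point overstatement needs k = 0.02 × 150/p. That is about 4 women (2.8%) at 72.3%, 6 women (4.0%) at 50% and about 28 women (18.9%) at 10.6%.

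**Scale.** The 95% half-width at n = 150, 1.96 × √[p(1 − p)/150], is 4.9 points at 10.6%, 8.0 at 50% and 7.2 at 72.3%. Only at a high response rate with 10% unrated does the q = 0 shift match the sampling error.

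**The case against.** The strongest objection is that few women can fall out this way. Protocol 11.3 asks for end-of-study procedures when a subject discontinues, and lists an adverse event as a reason separate from withdrawal by the subject. A woman who stops because of pain or bruising is therefore due a rating, and once rated she is in the population. SAP 3.2.2 also provides for a visit that takes place without injections, and four contacts after each session (Protocol 10.1) let the site learn of a departure. This stands. It confines the excluded group mainly to women who withdraw consent or are lost before Day 22.

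A second objection is that exclusions are visible. SAP 3.4.2 tabulates the size of each population against all enrolled subjects and lists those excluded, so a reader could work out the worst case for women never rated. This also stands, but it leaves the calculation to the reader. It does not help with a woman rated only at Day 22: she is in the population, but the SAP text does not say how she counts at Day 180. The table layouts are in SAP Module 2, which I have not seen.

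A third is that effectiveness is a secondary objective and is summarised descriptively, so no type I error or treatment contrast is affected. I agree.

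A reader might go further and infer that the rates are biased upward, or that the exclusion can only raise them. The documents do not support that. It would need some women to be unrated and their response to be lower than that of rated women. The documents give no dropout rate and no information on response among women who leave. Someone lost to follow-up may still have improved by a level.

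**Conclusion.** The point holds in a limited form. The stated rule removes injected, never-rated women from every effectiveness denominator, and no planned summary puts them back. The group is probably small because of the early-termination rating. The responder percentages can be biased upward, but only if these women respond less often than those rated.

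With 2% to 10% of 150 unrated and all of them non-responders, the overstatement is about 1 to 7 points at a response rate of 50% to 72%, and about 1 point or less near 10%. Both the unrated share and the response rates are assumptions. The primary safety analysis is unaffected, because SAP 3.3.1 keeps every injected woman.

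**What to change.** In SAP 3.4.6.1.2 and 3.4.6.2, add responder and satisfaction summaries over all injected subjects with a baseline CR-PCSS, which is in effect the safety population. Use that fixed N, by assigned region and overall, as the denominator at every visit. Count an unrated treatment area as a non-responder, and show the number not assessed in its own row, including in the Day 180 satisfaction table.

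Report these beside the planned effectiveness-population tables and label the planned ones observed-case. The population definition can stay as it is; replacing it outright would be harder to justify, because counting unrated women as failures is a conservative convention that can understate response. The fixed N also settles, for the added tables, how to count a woman who was rated early and missed later visits.

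The cost is a few lines of SAP text and one extra set of tables. The added rates will be slightly less favourable than the planned ones if anyone is unrated, and identical if no one is.

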5. SCHEDULE OF EVENTS

Procedures	Day -14 to -1 Screening	Day 1 (Baseline)	Post-Injection Day				Day 22 (±3 d)	Post-Injection Day				Day 43 (± 3 d)	Post-Injection Day				Day 90 (± 7d)	Day 180 (+ 7 d) EOS/ ET	Unsched. Visit
			1	3	6	13		1	3	6	13		1	3	6	13			
Informed Consent	X																		
Inclusion/Exclusion	X																		
Medical history/EFP history including previous treatments	X																		
Prior/concomitant medications/procedures	X	X	X	X	X	X	X	X	X	X	X	X	X	X	X	X	X	X	
Physical examination:	X																		
• Body weight	X						X ^a					X ^a				X	X	X	
• Height	X																		
• Fitzpatrick skin type	X																		
Vital signs	X	X ^b					X ^b					X ^b				X	X	X	
12-lead ECG	X																		
Digital Photography ^c		X	X	X	X	X	X	X	X	X	X	X	X	X	X				
Medical status follow-up			X	X	X	X		X	X	X	X		X	X	X	X			
Laboratory Assessments																			
• Clinical laboratory	X																X	X	
• Anti-AUX-I/anti-AUX-II antibody level		X ^a					X ^a					X ^a				X	X		
• Pregnancy testing	X ^f	X ^{a,f}					X ^{a,f}					X ^{a,f}				X ^f	X ^f	X	
Subject Cellulite Assessments																			
• Subject Satisfaction With Cellulite Treatment Assessment																	X ^g		
Investigator Cellulite Assessments																			
• Selection and marking of dimples to be treated within both assigned treatment areas		X ^a					X ^a					X ^a							
• Clinician Reported Photonumeric Cellulite Severity Scale (CR-PCSS)	X						X ^{a,e}					X ^{a,e}				X ^e	X ^e		
• Hexsel Cellulite Severity Scale (CSS)	X ^d																		
• Confirm Eligibility																			
• Assign Region	X																		
• Study drug administration		X					X					X							

Procedures	Day -14 to -1 Screening	Day 1 (Baseline)	Post-Injection Day				Day 22 (±3 d)	Post-Injection Day				Day 43 (± 3 d)	Post-Injection Day				Day 90 (± 7d)	Day 180 (+ 7 d) EOS/ET	Unsched. Visit
			1	3	6	13		1	3	6	13		1	3	6	13			
• Injection site reactions/local tolerability in assigned treatment areas		X	X	X	X	X	X	X	X	X	X	X	X	X	X	X	X		
• Adverse events	Monitored Throughout Study																		

- ^a Before injection.
 - ^b Up to 4 hours before injection; approximately 15 and 30 minutes after injection. Pulse and BP to be taken after subject has been sitting for 5 minutes. Vital signs must be stable before the subject is discharged.
 - ^c Applies only to sites participating in the photography sub-study. Photos are to be obtained before and after dimple marking on treatment visits.
 - ^d Initial Hexsel CSS at Screening must be ≤13 on at least 2 bilateral treatment areas, and confirmed at Day 1 visit.
 - ^e Assessment of each of the two assigned treatment areas only.
 - ^f Serum pregnancy test on Screening and Day 180/EOS/ET, and any Unscheduled Visits; urine pregnancy test on Day 1, Day 22, Day 43, and Day 90 visits
- d=Days; ECG=Electrocardiogram; EFP=Edematous fibrosclerotic panniculopathy

